The World Health Organization (WHO) has recently defined patient centeredness as a fundamental characteristic for the quality of health care (1). Patient centeredness can be measured through the collection of functional outcomes and quality of life reported by patients, the so-called Patient-Reported Outcome Measures (PROMs). The Organization for Economic Cooperation and Development (OECD) has launched an initiative (called PaRIS Initiative) for the systematic collection of PROMs in patients undergoing elective hip and knee prosthetic arthroplasty 6 and 12 months after surgery (2). Such data is already routinely collected in several OECD member countries that have implemented implant registries (3). The IRCCS Rizzoli Orthopedic Institute (IOR) was selected as a pilot center for the launch of the initiative, whose purpose is to accelerate the adoption and reporting of validated, standardised, internationally-comparable patient-reported indicators, particularly within patient registries. IOR was selected as a pilot center for the launch of the program in Italy because the Institute hosts the Registry of Orthopedic Prosthetic Implantology (RIPO) since 1990 (4). Given that RIPO also includes shoulder implants, the same data will be collected also for patients undergoing shoulder replacement.

OBJECTIVES OF THE STUDY

- 1) To monitor and analyze functional outcomes and quality of life reported by patients undergoing elective hip, knee and shoulder arthroplasty performed at the IOR;
- 2) To identify predictive factors influencing the evolution of patients-reported outcome measures.

STUDY DESIGN

Prospective cohort study.

METHODS

Setting of the study

The study will be carried out at 6 operative units of the IOR (Orthopedic and Traumatological I Clinic, Orthopedic and Traumatological Clinic II, Orthopedic and

Traumatologic Clinic III, Reconstructive Orthopedic Surgery - Innovative Techniques / Revision surgery of hip prosthesis and new implant development, Surgery of the Shoulder and Elbow, Orthopedics-Traumatology and Prosthetic Surgery and of hip and knee replanting). For patients accessing through the “hospitalization-before-surgery” pathway, the enrollment will take place in the specific ambulatory in the month preceding the intervention. The remaining patients will be enrolled directly at the operative Units involved.

Participants

Inclusion criteria:

1. Males and females aged 18-95 years

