2. Be on the list for an elective primary arthroplasty of hip, knee or shoulder
3. Availability to sign the informed consent

Exclusion criteria:

1. Severe cognitive impairment
2. To be listed for arthroplasty for musculoskeletal cancer
3. Not eligible for the surgical intervention

Procedures

The study consists of 3 phases:

1. **Baseline:** identification of eligible patients that the meet inclusion criteria. The evaluation will be performed in the pre-hospitalization ambulatory in the month preceding the intervention or in the ward at the time of hospitalization; in this phase it is planned also to:
 - present the study to the patients and collect the informed consents for study participation for the treatment of personal data
 - collect patients' authorization to be contacted by mail or by telephone for the follow-up.

- Administer and collect 2 questionnaires (EQ-5D for all subjects and the joint-specific questionnaire: hip, knee or shoulder).

The baseline includes two different ways of distributing and collecting questionnaires, based on the method of hospitalization:

- For patients in the “hospitalization-before-surgery” pathway (about 90% of the study population), RIPO personnel will go to the pre-admission ambulatory and will distribute and collect informed consents and questionnaires. Patient questionnaires administered to patient not eligible for intervention at a later stage will be destroyed.
- For patients not in the “hospitalization-before-surgery” pathway (about 10% of the population), the RIPO personnel will go directly to the operative units, after checking the day before the scheduled hospitalizations, and will distribute and collect informed consents and questionnaires.

The staff in charge of the distribution and collection of the questionnaires will put their data on the front page of the questionnaire and then they will be transformed into an identification code containing the initials of patients' name and surname followed by a progressive number. This code be used for data entry in the CRF and then to reconcile the patient record with RIPO unique pseudo-anonymized identification code.

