2. **6 and 12 months follow up:** the RIPO staff will send a mail containing the same 2 questionnaires described in the baseline phase together with an accompanying letter with the instructions and a pre-paid envelope; the subject will be asked to resubmit the questionnaires. It will be also indicated how to receive direct support by contacting the IOR. In the event that patients - after receiving the package with the follow-up questionnaires - do not send them within 1 month, they will be directly contacted by telephone.
3. **Data collection and processing** will be performed by the RIPO staff and the methodological and statistical support of the biomedical research and health services unit of the University of Bologna.

Questionnaires

Four validated questionnaires will be used in the study. One questionnaire (Euro Quality 5 Dimensions, EQ-5D) for the general assessment of patient's health status will be administered to all the patients in the study (5). Three other joint-specific questionnaires will be administered to patients depending on the surgery procedure they will be undergoing. The joint-specific questionnaires are: Hip disability and Osteoarthritis Outcome Score - Short Form (HOOS-PS) for patients undergoing hip replacement (6); Knee injury and Osteoarthritis Outcome Score - Short Form (KOOS-PS) for patients undergoing knee replacement (7); the American Shoulder and Elbow Surgeons Standardized Shoulder Assessment Form (ASES), for patients undergoing shoulder implants. This last questionnaire will be administered in a modified version that does not include the assessments performed by the orthopedic surgeon (8).

ENDPOINTS

The outcomes of interest are functional outcomes and quality of life, measured through the total scores and the subscales of the administered questionnaires.

In particular, for the joint-specific functional scales the total score will be used, while for the EQ-5D the scores of the single dimensions will be used, together with a total VAS score on a 0-100 scale, that measures the overall health status.

The type of intervention will be used to stratify patients into three groups (hip, knee and shoulder).

The socio-demographic and clinical variables of interest, such as sex, age, comorbidity, and patient's clinical history, will be extracted from the clinical records and the data recorded in the RIPO.

SAMPLE SIZE

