All patients hospitalized for elective hip, knee and shoulder prosthetic surgery at the 6 participating Operative Units will be included in the study. Based on the number of surgical procedures (i.e. implants) carried out in 2016, it is planned to recruit a total of 1700

patients, of which 1100 with hip replacement, 500 with knee replacement and 100 with shoulder replacement. A 10% rejection rate and a 40% follow-up loss are expected.

QUANTITATIVE VARIABLES

The quantitative variables of the study, which include the total scores of the scales and the subscales of the questionnaires, will be treated as such in the analyses and therefore not transformed.

STATISTICAL ANALYSES

Statistical analyses will be performed by the RIPO biostatistician in collaboration with the biostatistician of the methodological and statistical support unit for biomedical and on health services research of the Department of Biomedical and Neuromotor Sciences of the University of Bologna.

To analyze the evolution of the functional outcomes and quality of life of patients at 6 and 12 months from the surgery according to the type of intervention - and to identify predictive factors that influence this evolution - generalized estimation equations (GEE) and structural equation models (SEM) will be used. These techniques allow to obtain robust estimates even in the presence of missing data. We estimate an attrition rate of about 40% of cases, and non-compliance in resubmitting the questionnaires is hypothesized not to be linked to a systematic reason (for example the lower severity of patients). Therefore the missing data is to be considered completely random (MCAR).

Sensitivity analyses will be performed to assess whether the hypothesized mechanism of data loss at follow-up is supported by the data, or if alternative mechanisms need to be considered.

STUDY DURATION AND TIMELINE

The study will have an overall duration of 30 months and will be considered in any case completed 6 months after the recruitment target is achieved.

The study timeline is the following:

- Months 1-12: Selection and enrollment of the patients and database implementation.
- Months 6- 24: Follow up (6 and 12 months) and database implementation.

- Months 24-30: Analysis of data and dissemination of results.

The approval of the Ethics Committee will be considered as the start date of the study.

Study start date: 1/1/2019 (after approval by the Ethics Committee)

Enrollment start date: 1/1/2019

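### The scheduled follow-up phase ends at month 24, one to two months before the plan's own last 12-month contact steps, and no data cut-off is stated

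*Combined protocol and SAP*

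**What the plan says.** The combined protocol and SAP sets three phases under Study Duration and Timeline: "Months 1-12: Selection and enrollment of the patients and database implementation", then "Months 6- 24: Follow up (6 and 12 months) and database implementation", then "Months 24-30: Analysis of data and dissemination of results". The study lasts 30 months, from 1/1/2019 to 30/06/2021.

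Other sections fix when each contact takes place:

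- **Time origin.** Statistical Analyses refers to the "quality of life of patients at 6 and 12 months from the surgery", so the clock starts at surgery and not at enrolment.
- **Lag to surgery.** Under Setting of the study, for the pre-admission pathway, "the enrollment will take place in the specific ambulatory in the month preceding the intervention". Procedures, phase 1, agrees: "The evaluation will be performed in the pre-hospitalization ambulatory in the month preceding the intervention or in the ward at the time of hospitalization". It puts the pre-admission share at "about 90% of the study population), RIPO personnel will go to the pre-admission ambulatory". The other 10% or so are enrolled on the ward.
- **Telephone step.** Under Procedures, phase 2, patients receive the questionnaires by post, and if they "do not send them within 1 month, they will be directly contacted by telephone".

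A further sentence under Study Duration and Timeline treats the study as complete 6 months after the recruitment target is reached. The document gives no database lock, no last date for accepting questionnaires, and no rule on returns after month 24.

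**The concern.** A window closing at month 24 fits only if surgery takes place on the day of enrolment and every 12-month form comes back at once. The plan's own procedures allow up to 1 month before surgery and a 1-month wait before the call. Neither is in the window.

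The 12-month measurement of the last patients enrolled is at stake. If the phases are applied as scheduled, data entry stops and analysis starts while their contact procedure is unfinished. If they are applied loosely, data keep arriving during analysis with no stated lock. Staff cannot tell which is meant.

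Any loss would be selective. It would depend on enrolment date and would fall on people who do not reply unprompted, whom the telephone step exists to recover. It could add to the 40% attrition already expected, in a plan whose working assumption is that data are missing completely at random.

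**Working it through.** **Inputs.** Enrolment ends at month 12 and follow-up at month 24 (Study Duration and Timeline). Lag from enrolment to surgery, *g*: 0 to 1 month for 90% of patients and about 0 for 10% (Setting of the study; Procedures, phase 1). Wait before the call: 1 month (Procedures, phase 2). Planned recruitment: 1700 (Sample Size). Even accrual over 12 months is my assumption.

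**The plan's figure.** 12 months of enrolment + 12 months of follow-up = month 24. It reproduces, but only with zero lag and no return or telephone time. The 30-month total also reproduces from the two dates.

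**Last patient enrolled (month 12).**

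| 12-month step | Formula | *g* = 0 | *g* = 0.5 | *g* = 1 |
|---|---|---|---|---|
| Mailing | 12 + *g* + 12 | 24 | 24.5 | 25 |
| Telephone | 12 + *g* + 12 + 1 | 25 | 25.5 | 26 |

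Even with zero lag, the telephone step for patients enrolled in month 12 falls after month 24. The wait counts from receipt of the package, so postal time would add slightly to these figures.

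The 6-month contact is not affected: its last telephone step is at 12 + 1 + 6 + 1 = month 20.

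**Share of the cohort with a step after month 24.** Here *g* is the mean lag in the pre-admission pathway.

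- Mailing: 0.9 × *g* / 12. Only pre-admission patients enrolled in at most the last month contribute.
- Telephone: [0.9 × (*g* + 1) + 0.1 × 1] / 12 = (0.9*g* + 1) / 12. This covers enrolment in the last 1 to 2 months.

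| Mean lag *g* | Mailing late | Telephone step late, if needed | Of these, needing the call if 40% do |
|---|---|---|---|
| 0 | 0 | 1/12 = 8.3% → 142 | 57 |
| 0.5 | 0.45/12 = 3.75% → 64 | 1.45/12 = 12.1% → 205 | 82 |
| 1 | 0.9/12 = 7.5% → 128 | 1.9/12 = 15.8% → 269 | 108 |

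The last column is 0.4 times the unrounded telephone count. The plan does not give the share who fail to return the form within a month. The 40% is borrowed from its expected loss to follow-up, for illustration only.

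**Room within the study.** Month 26 is 4 months before the study ends at month 30.

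**The completion rule.** If the target is reached at month 12, the study is complete at 12 + 6 = month 18. With zero lag, the 12-month mailing then falls after completion for everyone enrolled after month 6: 1700 × 6/12 = 850.

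**The case against.** The best defence is that the timeline is a coarse planning list. Its phases overlap: months 6-12 belong to both enrolment and follow-up, and month 24 to both follow-up and analysis. The telephone procedure carries no calendar limit, and the study runs to month 30, so calls at months 25-26 could be made and their data used.

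Much of this stands. A reader might infer that late responders are cut off and their 12-month outcomes lost. The document does not support that, because nothing in it sets a data cut at month 24 or excludes later returns. A reader might also treat the 205 as lost telephone contacts. They are patients whose call would be late if needed, and the call is made only to those who have not replied within a month. Nor should the full 1-month lag be applied to all 1700, since about 10% are enrolled on the ward with essentially no lag.

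The defence does not remove the mismatch. Data entry is scheduled only to month 24 and analysis starts then, yet the stated contact steps cannot finish by that month on any permitted lag. The lack of a lock date leaves the conflict unresolved.

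It is also fair to say that a longer window achieves nothing while the completion rule stands. That is a reason to edit both together: the window is too short even without that rule.

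**Conclusion.** The point holds as a scheduling conflict. The follow-up and database phase ends 1 to 2 months before the last 12-month contact steps. The last mailing falls at months 24-25 and the last telephone step at months 25-26.

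The counts rest on even accrual of 1700, a 90/10 pathway split and a central mean lag of half a month. The number actually needing a late call also rests on the assumed 40%. Slower or faster accrual near month 12 would change the counts but not the calendar conflict. Loss of these responses is a risk if the schedule is enforced, not a stated consequence. This should be corrected, but it does not by itself undermine the study.

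**What to change.** 1. Extend the follow-up and database line to at least month 26 plus return time. For example, months 6-27: questionnaires at 6 and 12 months after surgery, with the 1-month return period, telephone contact and data entry included.
2. Start final analysis after that, for example months 27-30.
3. State that database lock follows the last patient's 12-month telephone step, and how any later return is handled.
4. In the same edit, reconcile the sentence that completes the study 6 months after the recruitment target. The longer window is not secured while that rule stands.

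The 30-month duration and the 30/06/2021 end date do not change. The cost is a change of timeline wording and about 2 to 3 months less for final analysis. Programming can begin at month 24 on the data then available, which recovers part of that time.
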